If a haemostatic response to treatment cannot be achieved (i.e. the bleed does not stop) within 48 hours after initiating treatment with N8-GP, another FVIII product may be selected at the discretion of the investigator, and the patient must be withdrawn from the trial.

If a bleeding episode occurs on a planned prophylaxis dosing day before administration of the prophylaxis dose, or if a bleeding episode extends into such a day, the bleeding episode must be treated with the full prophylaxis dose (this dose should be recorded as treatment of a bleeding episode) (does not apply for surgeries). The patient should at all times follow the original prophylaxis dosing scheme unless a dose has already been given to treat a bleeding episode during the same day.

Treatment of bleeding episodes with N8-GP will be included in the overall count of ED.

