5.3.6 Treatment of patients with FVIII inhibitors

Approximately 20–30% of PUPs with severe haemophilia A develop inhibitors to infused FVIII rendering use of such replacement therapy ineffective. Patients who develop inhibitory antibodies remain at higher risk for morbidity and mortality associated with recurrent or uncontrolled bleeding events.

The majority of haemophilia patients with inhibitors develop high-titre (> 5 BU) inhibitors, and demonstrate an anamnestic rise in their inhibitor titre when re-exposed to FVIII. In these patients even frequent, high-dose FVIII substitution therapy becomes ineffective in controlling bleeding episodes as the infused coagulation factor products are neutralised by the inhibitor. Administration of FVIII bypassing agents (rFVII or activated prothrombin complex concentrates) becomes necessary for treatment of bleeding episodes.

Treatment of bleeding episodes with by-passing agents, i.e. rFVIIa or APCC according to local standard care, is allowed for patients who develop FVIII inhibitors within this trial. By-passing agents are not considered trial medication.

The ultimate goal of treatment in patients with high-titre inhibitors is to permanently eradicate the inhibitor by immune tolerance induction therapy (ITI), thereby making it possible for the patient to be treated routinely with FVIII replacement therapy. The therapeutic concept is based on long-term uninterrupted high exposure to FVIII in an effort to sufficiently tolerize the immune system. In that state, the clinical responsiveness to FVIII replacement therapy is restored.

Based on the available evidence, all patients with high-titre inhibitors (> 5 BU) should undergo ITI using the same type of product that the patient was using at the time of inhibitor development. This approach is supported by an international expert panel which concurred with treatment guidelines which recommend that ITI should be conducted with the same concentrate as the one against which antibodies were developed. This should ensure successful tolerance induction and reduce the risk of further inhibitor development to new molecules. It may therefore be expected that N8-GP will be favourable over the use of commercially available FVIII products for ITI in patients who developed FVIII inhibitors within this trial.

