6.4 Withdrawal criteria

The patient may withdraw at will at any time either by the patient or by the patient's parent(s) or the patient's LAR. The patient's request to discontinue must always be respected.

Protocol v 1 | 36 of 114

The patient may be withdrawn from the trial at the discretion of the investigator due to a safety concern or if judged non-compliant with trial procedures.

The patient must be withdrawn if the following applies:

- 1. Dosed in the trial, but not fulfilling the inclusion and/or exclusion criteria
- 2. Anaphylactic reaction to the trial product, for definition see Section 11.1
- 3. Major surgery before 50 EDs, see Section 5.3.4
- 4. Significant thromboembolic event, see Section 11.1
- 5. Incapacity or unwillingness to follow trial procedures
- 6. Use of coagulations factors other than N8-GP or anti-coagulants unless in relation to ITI
- 7. ITI treatment has not been started within 6 months from the date of confirmation of positive FVIII inhibitor (BU $\geq 0.6/\text{mL}$)
- 8. FVIII inhibitor titre decline from peak level is less than 20% after 12 months of ITI treatment
- 9. FVIII inhibitor is positive (BU $\geq 0.6/\text{mL}$) after 24 months of ITI treatment.
- 10. After completed ITI treatment (maximum 24 months), prophylaxis treatment as described in the protocol is not resumed/started.

If a patient experiences treatment failure where haemostatic response is rated as none according to Section 8.6, the investigator should consider if it is in the patient's best interest to continue in the trial.

All data collected prior to withdrawal may be used in the trial analyses if considered relevant by Novo Nordisk.

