8.2.3 Treatment of bleeding episodes in inhibitor patients

Bleeding episodes in inhibitor patients that do not respond sufficiently to N8-GP treatment may be treated with by-passing agents according to local practice.

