Assessment for FVIII inhibitors will be carried out using a heat modified Nijmegen FVIII Bethesda assay analysed at the central laboratory. The assay is validated according to international recognised guidelines. The assay is based on measurement of the FVIII activity (inhibitory activity) in plasma samples mixed with a fixed amount of normal plasma pool in buffer. Inhibitors will be

Protocol v 1 | 56 of 114

Protocol Date: 04 November 2013 Novo Nordisk
Trial ID: NN7088-3908 Version: 1.0

UTN: U1111-1148-1897 CONFIDENTIAL Status: Final Page: 57 of 114

considered: $0.6 \text{ BU} \le \text{low titre inhibitor} \le 5 \text{ BU}$, high titre inhibitors are defined as > 5 BU. Inhibitors will be recognised by comparison to a clinical cut-point of $\ge 0.6 \text{ BU}$.

If FVIII inhibitor development is suspected during the course of the trial due to for instance increased number of bleeding episodes, bleeding episodes difficult to treat, recovery and trough levels below expected values or a positive local inhibitor test, the patient must attend an unscheduled visit as soon as possible and a plasma sample must be shipped to the central laboratory for inhibitor analysis.

Any sampling for the inhibitor test must be performed at least 4 days after last administration of N8-GP to allow for wash-out of the drug.

If the result of the inhibitor test is positive, a second confirmatory inhibitor test should be performed by the central laboratory. The confirmatory samples should be collected as soon as possible, but no sooner than 4 days after the last dose of N8-GP. Assessments of FVIII activity (recovery) and binding antibodies must be performed. If considered relevant a lupus anticoagulant test can be performed.

A positive confirmed inhibitor is considered to have disappeared if the inhibitor titre is < 0.6 BU on 2 consecutive inhibitor tests (performed with 1 month intervals) and the FVIII recovery is $\ge 66\%$ of expected values. A patient with repeated positive test result will count only once in the determination of the inhibitor incidence rate.

If an investigator decides to perform inhibitor testing locally, he/she must send a duplicate sample for inhibitor testing at the central laboratory. The results from the central laboratory will be used in the analysis of trial data. A positive inhibitor test must always be reported as a MESI irrespective of the test being performed locally or at the central laboratory (refer to Section 11.2).

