5.3.6 Treatment of patients with FVIII inhibitors

Patients who develop FVIII inhibitors during this trial may receive N8-GP and/or Treatment of bleeding episodes with by-passing agents, e.g. i.e. rFVIIa or APCC for treatment of bleeding episodes according to local standard care is allowed for patients who develop FVIII inhibitors within this trial. However, N8-GP dose levels used should not exceed 75 U/kg as a single dose and not exceed 200 U/kg as a maximum 24 hour dose. Treatment with FVIII concentrates other than N8-GP is not allowed. By-passing agents are not considered trial medication.

The ultimate goal of treatment in patients with high-titre inhibitors is to permanently eradicate the inhibitor by immune tolerance induction therapy (ITI), thereby making it possible for the patient to be treated routinely with FVIII replacement therapy again. The therapeutic concept is based on long-term uninterrupted high exposure to FVIII in an effort to sufficiently tolerise the immune system. In that state, the clinical responsiveness to FVIII replacement therapy is restored.

Novo Nordisk plans that Patients who develop inhibitors, within this trial, will be offered continued treatment with N8-GP, including ITI for a maximum of 24 months. ITI with N8-GP will not be initiated until Novo Nordisk has reviewed the clinical data available after completion of the N8-GP pivotal and surgery trial (pathfinderTM2 and pathfinderTM3), and of the paediatric PTP trial (pathfinderTM5) data needed for opening the paediatric PUP trial according to EMA requirements.

It is expected to use a N8-GP dosing regimen for ITI similar to local standard care/guidelines applied for ITI with marketed FVIII products. For each individual patient, ITI regimens with N8-GP would have to be reviewed by the investigator every month, and more formally reviewed every 3 months by Novo Nordisk.

If patients with (usually low titre) inhibitors respond well to treatment with N8-GP then the patient can continue the prophylaxis. These patients can still start ITI treatment within 6 months after the

Protocol Amendment
Trial ID: NN7088-3908

CONFIDENTIAL

Date: 20 March 2015 | Novo Nordisk
Version: 2.0

UTN: U1111-1148-1897 CONFIDENTIAL Status: Final Page: 14 of 41

confirmatory inhibitor test. If the inhibitor is still present (BU>/=0.6) at 6 months after the confirmatory test the patient must start ITI or withdraw from the trial.

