8.1.11 ITI Visit

In case of high titre FVIII inhibitor (>5BU) confirmed by central laboratory the investigator must decide how to proceed with treatment. Novo Nordisk will communicate when ITI is allowed in this trial, see Section 5.3.6. ITI with N8-GP must be initiated within 6 months of the confirmatory inhibitor test. The used N8-GP dose and dosing regimen is at the discretion of the investigator but should not exceed 75 U/Kg for a single dose, and not exceed a total daily dose of 200 U/Kg. Bypassing agents can be used to treat bleeding episodes.

If ITI is initiated, the patient will follow a visit schedule prescribed by the investigator and according to local standard of practice. Monthly visits are recommended, and the below listed assessments are recommended to be performed:

• Bleeding episode evaluation (only if treatment with N8-GP)

Reminder

• Follow up on any AEs according to Section 11.2

^{*} Surgery and PK session can also be performed during a regular visit but are to be registered under unscheduled visits.

20 March 2015 | Novo Nordisk Protocol Amendment Date: Trial ID: NN7088-3908 Version: 2.0 CONFIDENTIAL Final

Status:

25 of 41

Page:

UTN: U1111-1148-1897 EudraCT No.: 2013-004025-88

After ITI treatment, when the inhibitor is confirmed to be negative, a FVIII recovery test should be performed to confirm the recovery. A dose of 60 U/Kg should be used. Before returning to regular prophylaxis treatment a PK session must be performed after a 72 hours treatment-free wash-out period, see Section 8.4.2.2 for PK session details.

For patients returning to regular prophylaxis N8-GP treatment, the visit schedule is taken up from where the patient left the visits according to Table 2-1. The patient must not attend the same visit number twice. V9 end of main phase Table 2-1 even when the corresponding total ED does not match.

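### Withdrawal criterion 6 conflicts with the permission to give by-passing agents to inhibitor patients, and exit after an uncontrolled bleed is not tied to the confirmatory inhibitor test

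*Combined protocol and SAP*

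**What the plan says.** **Withdrawal rules.** In 5.3.3, if a bleed has not responded within 48 hours of starting N8-GP, "another FVIII product may be selected at the discretion of the investigator, and the patient must be withdrawn from the trial". The sentence does not mention inhibitor testing. Section 6.4 lists as mandatory criterion 6 "Use of coagulations factors other than N8-GP or anti-coagulants unless in relation to ITI", and Amendment 2 keeps it. An uncontrolled bleed is not itself a criterion in 6.4. After a response rated none, the investigator considers whether it is in the child's "best interest to continue in the trial".

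**By-passing agents.** Section 5.3.6 of protocol version 1.0 says that treating bleeds with them "is allowed for patients who develop FVIII inhibitors within this trial". The Amendment 2 wording opens "Patients who develop FVIII inhibitors during this trial may receive N8-GP and/or" and goes on to name by-passing agents. Section 8.2.3 says that bleeds in inhibitor patients that "do not respond sufficiently to N8-GP treatment may be treated with by-passing agents according to local practice". Section 8.1.11, as amended, states that "ITI with N8-GP must be initiated within 6 months of the confirmatory inhibitor test" and in the same paragraph permits by-passing agents for bleeds.

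**Inhibitor testing.** Section 8.4.2.2 gives bleeds that are hard to treat as one reason to suspect an inhibitor, in which case "the patient must attend an unscheduled visit as soon as possible and a plasma sample must be shipped to the central laboratory". A positive result should be followed by a confirmatory central test, at least 72 hours after the last N8-GP dose (Amendment 2). Section 3.3 defines a case by two positive central tests in a row. Table 2-1 marks an inhibitor test at the end-of-trial (EOT) visit.

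**Analysis.** Section 16.3 divides patients with inhibitors by all patients with at least 10 exposure days (EDs), adding those with fewer EDs who have an inhibitor, and gives an exact one-sided 97.5% upper limit. The high-titre rate (16.4.2.3) is handled in the same way.

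**The concern.** Two rules remove children from the trial in a situation where an inhibitor is either known or plausible, and neither refers to the inhibitor pathway.

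The first is a contradiction. A child with an inhibitor may be given a by-passing agent under three sections and must be withdrawn for it under a fourth, unless the dose relates to ITI. At stake are continued follow-up and the ITI outcome data, not the primary rate.

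The second is a missing link. A bleed uncontrolled on N8-GP at 48 hours is itself a reason to suspect an inhibitor, yet the exit that follows is not made to wait for, or include, the second test that defines a case. If a true case left with one positive result, the primary rate and its upper limit would be too low, which is the favourable direction for a safety endpoint. The high-titre rate is exposed in the same way.

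**Working it through.** **Step 1: criterion 6 against the permissions.**

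- Criterion 6 covers coagulation factors other than N8-GP and exempts only use related to ITI.
- ITI may begin up to 6 months after the confirmatory test (8.1.11), so by-passing doses can be needed before any ITI exists.
- Amendment 2 lets inhibitor patients who respond well continue prophylaxis (5.3.6). Amended criterion 7 keeps those whose inhibitor disappears within 6 months. Such a child may never have ITI, so even a broad reading of the exemption does not cover a by-passing dose given to him.
- Section 8.9 refers the reader to 8.2.3 for by-passing agents. That shows the intent but does not change criterion 6.

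The conflict is therefore in the current text.

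**Step 2: how far the two tests are secured for a child leaving under 5.3.3.**

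- First test: mandatory once an inhibitor is suspected (8.4.2.2). Sites must also be able to test locally (8.4.1.1, Amendment 2), with a duplicate sent to the central laboratory.
- Second test: a recommendation in form. The wash-out is counted from N8-GP only, although the child may by then have received another FVIII product.
- EOT visit: has one inhibitor test, which can be the second if an earlier sample was positive. The visit is to be pursued with every effort but is not guaranteed, and no visit is scheduled after it.
- No sentence ties the confirmatory sample to exit.

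**Step 3: what one unconfirmed case does to the rate.** The plan gives no figure on this point. Its only computed size, 125 starters, is 100/(1 − 0.20) = 125, which reproduces but does not bear on this.

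Inputs: a rate of about 30% (11.6.2), or 20% as the low end of the range in 5.3.6. I assume n = 50 and n = 100, because the amendment log expects between 50 and 100 completers. With x cases among n, the upper limit is the 0.975 quantile of Beta(x + 1, n − x). A case not recognised stays in the denominator with at least 10 EDs, and leaves both counts with fewer.

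| Assumed truth (upper limit) | One case missed, at least 10 EDs | One case missed, fewer than 10 EDs | Fall in rate, points |
|---|---|---|---|
| 15/50 = 30.0% (44.6%) | 14/50 = 28.0% (42.5%) | 14/49 = 28.6% (43.3%) | 2.0 or 1.4 |
| 10/50 = 20.0% (33.7%) | 9/50 = 18.0% (31.4%) | 9/49 = 18.4% (32.0%) | 2.0 or 1.6 |
| 30/100 = 30.0% (40.0%) | 29/100 = 29.0% (38.9%) | 29/99 = 29.3% (39.3%) | 1.0 or 0.7 |
| 20/100 = 20.0% (29.2%) | 19/100 = 19.0% (28.1%) | 19/99 = 19.2% (28.3%) | 1.0 or 0.8 |

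**The case against.** The strongest reply is that the plan already handles most of this.

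- **Intent on by-passing agents is clear.** Several sections allow them, Amendment 2 records them as concomitant medication, and 8.9 points to 8.2.3. This stands as evidence of intent. It does not alter a mandatory criterion that a site or monitor may apply as written.
- **The confirmatory rule is general.** It does not exclude leavers, the EOT visit must be actively sought, and its test can serve as the second. This stands, and it narrows the gap to children whose second sample is never drawn or is compromised by replacement FVIII.
- **Such children are not invisible.** Any positive test, and any clinical sign of inhibitor formation, is reported as a medical event of special interest (8.4.2.2, 11.1) and summarised (16.4.2.5). Withdrawal reasons are sought. This stands too, but that table does not feed the primary rate.
- **16.3 does not say confirmed.** A literal reader might count a single positive. The definition in 3.3 points the other way, so the likely treatment is as a non-case. The ambiguity is a further reason to state the rule.
- **The effect is small.** At 15/50 the limit lies 44.6 − 30.0 = 14.6 points above the estimate, and 16.3 tests no hypothesis. This stands and sets the severity.

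A reader might go further and infer that every leaver after an uncontrolled bleed should be treated as a possible inhibitor case. Amendment 8 describes transient low recovery in early EDs without detectable inhibitors, so failure of N8-GP is not enough to presume an inhibitor in an untested child.

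**Conclusion.** The point holds and is minor. The conflict between criterion 6 and 5.3.6, 8.2.3 and 8.1.11 is certain on the text. The confirmatory-test gap is real but conditional: it needs a true case, switched to another FVIII product, who leaves with one positive central test and no valid second one. Each such child lowers the rate by 1.4 to 2.0 points at an assumed n = 50 and 30%, and by 0.7 to 1.0 points at n = 100. This rests on reading 16.3 with the two-test definition in 3.3.

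Three stronger readings are tempting but unsupported:

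- That criterion 6 removes confirmed cases from the primary rate. It does not; they have already been counted, and only later follow-up and ITI data are at risk.
- That 5.3.3 withdraws every child with an uncontrolled bleed. The natural reading, given 6.4, is that withdrawal follows actual use of another FVIII product, although 5.3.3 should say so.
- That the primary rate is biased by a known amount. The documents give no number of such children, and scheduled tests from ED 5 to ED 50 narrow the window, so no total can be derived.

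**What to change.** 1. **Criterion 6 (6.4):** exempt by-passing agents given under 5.3.6 or 8.2.3 for a confirmed or suspected inhibitor.
2. **Section 5.3.3:** state that withdrawal follows actual use of another FVIII product and cross-refer to 8.4.2.2. Require that any positive sample be followed by the confirmatory central sample at or before the EOT visit, with wash-out of any replacement FVIII taken into account. Rescue treatment must not wait for this.
3. **Section 16.3:** report how many children leave with an incomplete inhibitor work-up. Add one sensitivity rate that counts leavers with a single unconfirmed positive central test as cases in both numerator and denominator. Report untested leavers as a count only; do not impute them as cases.

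The cost is wording in two sections, one or two blood samples per affected child, and one extra count and one rate in the primary table. The sensitivity figure may look slightly less favourable: in the n = 50 example it would return 14/50 or 14/49 to 15/50.

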5.3.4 Treatment of suspected bleeding episodes

In case of an abdominal or head trauma where there is a risk of a severe traumatic bleeding episode it is allowed to initiate treatment before clinical symptoms arise. This is defined as preventive treatment of suspected severe traumatic bleeding episode. The recommended dose is equivalent to treatment of a severe bleeding episode

Protocol v 1 | 30 of 114

Status:

Page:

Final

31 of 114

UTN: U1111-1148-1897 EudraCT No.: 2013-004025-88

5.3.5 Surgery

Minor surgeries, dental extractions and placement of central venous access ports can be performed while participating in this trial by administering extra doses of N8-GP equivalent to the dose for a severe bleeding episode (see Table 5–1), or aligned to local standard of practice, or guidelines for treatment of patients with haemophilia A with FVIII in the perioperative period.

Major surgery will only be allowed after the individual patient has reached 50 N8-GP EDs, and upon completions of the pathfinderTM3 surgery trial (NN7088-3860). The treatment regimen for major surgery will be based on results from the pathfinderTM3 surgery trial (NN7088-3860) and PK data obtained in the pathfinderTM5 trial (NN7088-3885) in paediatric PTPs. Novo Nordisk will communicate when major surgeries are allowed in this trial.

Definition of minor surgery

Minor surgery is defined as an invasive operative procedure where only the skin, the mucous membranes or superficial connective tissue is manipulated. For this trial, examples of minor surgery include:

- Implanting and removing ports in subcutaneous tissue
- Skin excisions
- Drainage of abscess
- Simple dental procedures
- Circumcision

Definition of major surgery

Major surgery is defined as any invasive operative procedure that require several days of FVIII substitution therapy and/or where any one or more of the following occur:

- A body cavity is entered
- A mesenchymal barrier (e.g., pleura, peritoneum or dura) is crossed
- A fascial plane is opened
- An organ is removed
- When normal anatomy is operatively altered
- Major elective orthopaedic surgery

Treatment with N8-GP during surgery will be included in the overall count of N8-GP EDs. Upon completion of the surgical/invasive procedure the patient can continue prophylaxis treatment with N8-GP as before the surgery.

Protocol v 1 | 31 of 114

Status:

Page:

Final

32 of 114

UTN: U1111-1148-1897 EudraCT No.: 2013-004025-88

